8.3.2 Continuous Endpoints

For continuous endpoints, missing data will be handled using the following approaches:

- The primary approach is Multiple Imputation Incorporating Return-to-Baseline to Handle Visits After UC-related Rescue Medication Use (RTB-MI). To assess the potential departures from the missing-at-random (MAR) assumption for visits after the intercurrent event of UC-related rescue medication use (see section 8.2.2), the Return-to-Baseline (RTB)^{4,5} approach which assumes subjects received UC-related rescue medication will have a washout "return to baseline" of any potential treatment effect, will be performed as following:
 - Step 1: after setting data after the intercurrent event of UC-related rescue medication use as missing, missing values due to all causes will first be imputed via MI under the MAR assumption.
 - Step 2: subject's efficacy assessments after the intercurrent event of UC-related rescue medication will be assumed to have returned to baseline. For each imputed dataset, missing change from baseline data due to the intercurrent event of UC-related rescue medication will be replaced by a value from a normal distribution $N(0, V_c)$, where V_c is the variance of change from baseline estimated from all observed values regardless of treatment groups, excluding those after UC-related rescue medication use.
 - Step 3: For each imputed dataset, the MMRM/ANCOVA model described in Section 8.1 will be applied to each completed set and the inference will be drawn using Rubin's combination rules (SAS proc MIANALYZE).
- MMRM/ANCOVA: Assuming any unobserved data (including the missing due to the intercurrent event of UC-related rescue medication use) can be considered as MAR, an MMRM/ANCOVA model excluding data after the

intercurrent event of UC-related rescue medication use will be performed as a sensitivity analysis.

- Delta-Based Multiple Imputation (DBMI).⁶ A missing-not-at-random (MNAR) model that varies assumptions for data after the intercurrent event of UC-related rescue medication use will be implemented through Delta-Based Multiple Imputation (DBMI). The DBMI is two-dimensional, i.e., assumptions about the missing outcomes on the upadacitinib treatment groups and the placebo group are allowed to vary independently. After setting data after the intercurrent event of UC-related rescue medication use as missing, missing values due to all causes will first be imputed via MI under the MAR assumption, and then a shift parameter (i.e., delta) will be applied to the imputed values for the missing data due to UC-related rescue medication use. For each pair of deltas, the MMRM/ANCOVA model described in Section 8.1 will be applied to each completed set and the inference will be drawn using Rubin's combination rules (SAS proc MIANALYZE). For each endpoint to be analyzed, the analysis will be repeated for a range of delta values corresponding to 0 to $\pm 100\%$ of the unadjusted mean observed for all subjects.
- As Observed (AO): The AO analysis will not impute values for missing evaluations, and thus a subject who does not have an evaluation on a scheduled visit will be excluded from the AO analysis for that visit. AO will include all values collected in the study regardless the occurrence of UC-related rescue medication intercurrent event.

8.4 Primary Efficacy Endpoint and Analyses

8.4.1 Primary Efficacy Endpoint

The primary efficacy endpoint is the achievement of clinical remission per Adapted Mayo score at Week 52. The primary estimand is the difference in the percentage of subjects achieving clinical remission per Adapted Mayo score at Week 52 regardless of premature discontinuation of study drug and without use of UC-related rescue medications (See Section 8.2.2) in the upadacitinib 15 mg QD, upadacitinib 30 mg QD and placebo groups in the ITT_A population. Details of the estimand definition are outlined in [Appendix E](#).

8.4.2 Handling of Missing Data for the Primary Efficacy Endpoint

The NRI-C will be the primary approach for missing data handling in the analyses of the primary efficacy endpoint.

The NRI-NC and HMI approaches will be used as sensitivity analyses.

8.4.3 Primary Efficacy Analysis

The primary analysis will compare the proportion of subjects achieving clinical remission in each upadacitinib treatment group and placebo group in the ITT_A population. The difference between the treatment groups in the primary efficacy endpoint will be assessed using the CMH test and will be stratified Bio-IR status (Bio-IR or Non-Bio-IR) at the Baseline of the Induction Study, clinical remission status at Week 0 (yes or no), and corticosteroid use at Week 0 (yes or no). A CMH based two-sided 95% confidence interval for the difference between treatment groups will be calculated.

8.4.4 Additional Analyses of the Primary Efficacy Endpoint

For the primary efficacy endpoint, the same CMH analysis as detailed in Section 8.1 will be repeated performed using As Observed (AO) data handling without any imputation as an additional analysis. The analysis will be conducted on the ITT_A population who have the efficacy measurement at Week 52 visit.

For the primary efficacy endpoint, a supplementary analysis will be conducted to evaluate the potential impact of deviations. In this analysis, subjects with deviations that could potentially impact the analysis of primary endpoint will be excluded. The criteria will be fully defined in the classification plan and the Exclusion of subjects will be adjudicated by the therapeutic area medical director (TAMD) and reasons for the subjects to be excluded will be documented and finalized before the Maintenance Study database lock for the primary analysis. Treatment difference between each upadacitinib treatment group and placebo with point estimate and 95% CI using NRI-C approach with the CMH method as detailed in Section 8.1.

8.5 Secondary Efficacy Analyses

8.5.1 Key Secondary Efficacy Analyses

The key secondary endpoints are defined in Section 3.2. The estimands corresponding to the secondary efficacy endpoints are defined in Section 2.1. Details of the estimand definitions are outlined in Appendix E. For ITT_A population, the key secondary efficacy endpoints will be analyzed by comparing each upadacitinib treatment group and placebo group. The binary secondary endpoints will be analyzed by CMH and the corresponding analyses are defined in Section 8.3.1. The NRI-C will be the primary approach for missing data handling in the analyses of binary secondary efficacy endpoints. The NRI-NC approach will be used as sensitivity analyses.

Continuous secondary endpoints will be analyzed by ANCOVA model with RTB-MI approach to handle the missing data due to UC-related rescue medication use as described in Section 8.3.2.

8.5.2 Additional Analyses of the Secondary Efficacy Endpoints

The secondary efficacy endpoints will also be analyzed for ITT_A population using As Observed (AO) data handling without any imputation. The binary endpoints and continuous endpoints will be analyzed by CMH and ANCOVA, respectively, and the corresponding analyses are specified in Section 8.1.

In addition, the continuous endpoints will be analyzed by ANCOVA (excluding data after rescue medication use) and DBMI method. Details are specified in Section 8.3.2.

8.6 Additional Efficacy Analyses

Additional efficacy endpoints are defined in Section 3.3.

The estimands corresponding to the additional efficacy endpoints are defined for each of the binary additional endpoints as follows: difference in percentage of subjects achieving binary endpoints regardless of premature discontinuation of study drug and without use of

UC-related rescue medications (See Section 8.2.2) in the upadacitinib 15 mg QD, upadacitinib 30 mg QD and placebo groups in the ITT_A population.

The estimands corresponding to the additional efficacy endpoints are defined for each of the continuous additional endpoints as follows: difference in mean change from baseline regardless of premature discontinuation of study drug and if subjects would not use UC-related rescue medications (See Section 8.2.2) in the upadacitinib 15 mg QD, upadacitinib 30 mg QD and placebo groups in the ITT_A population.

The estimands corresponding to UC-related hospitalization and surgery incidence rates is as follows: difference in the incidence rate through Week 52 regardless of premature discontinuation of study drug or use of UC-related rescue medications in the upadacitinib 15 mg QD, upadacitinib 30 mg QD and placebo groups in the ITT_A population.

For ITT_A population, additional efficacy endpoints will be analyzed by comparing each upadacitinib treatment group and placebo group. The binary endpoints and change from baseline continuous endpoints will be analyzed by CMH and RTB-MI with MMRM/ANCOVA, respectively, and the corresponding analyses are specified in Section 8.3. Change from maintenance baseline continuous endpoints will be analyzed by ANCOVA. The NRI-C approach will be used for missing data handling in the analyses of binary efficacy endpoints. For incidence rate of UC-related hospitalization and surgery during the Maintenance Study, adjusted incidence rates will be used to compare the risk between each upadacitinib treatment group and placebo group. Adjusted rates will be calculated as the number of subjects with the respective event divided by the time at risk. For subjects with an event during the Maintenance Study, time at risk is the patient-years (PYs) from Week 0 to the first event. For subjects without event, time at risk is PYs from Week 0 to the end of 30-day follow up period. Relative risk ratios of the incidence rates and confidence intervals will be calculated to evaluate the statistical significance of the difference between each upadacitinib treatment group and placebo group using z-score normal approximations. For multi-level categorical endpoints PGIC and PGIS, percentage of each outcome category will be reported descriptively, and no statistical comparison will be performed.

For ITT_B, ITT_C and ITT_E populations, the primary and secondary endpoints (specified in Section 3.1 and Section 3.2) will be summarized and descriptive statistics will be provided. The approaches of NRI-C and RTB-MI with MMRM/ANCOVA will be used for missing data handling in the analyses of binary and continuous efficacy endpoints, respectively.

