3.3 Additional Efficacy Endpoints

The following additional efficacy endpoints will be evaluated:

- The achievement of clinical remission per Partial Mayo score and corticosteroid free over time among subjects taking corticosteroid at Baseline in the Induction Study;
- The achievement of clinical remission per Adapted Mayo score and corticosteroid free at Week 52 among subjects taking corticosteroid at Baseline in the Induction Study;
- The achievement of clinical remission per Adapted Mayo score at both Maintenance Baseline and Week 52, and corticosteroid free for ≥ 90 days

immediately preceding Week 52 among subjects taking corticosteroids at Baseline in the Induction Study;

- The achievement of SFS ≤ 1 (and not worse than Baseline), RBS = 1 at both Week 36 and Week 44, clinical remission per Adapted Mayo score at Week 52 and corticosteroid free for ≥ 90 days immediately preceding Week 52 among subjects taking corticosteroids at Baseline in the Induction Study;
- The achievement of clinical remission per Full Mayo Score at Week 52;
- The achievement of clinical remission per Partial Mayo score over time;
- The achievement of clinical response per Partial Mayo score over time;
- The achievement of clinical remission per Adapted Mayo score over time;
- The achievement of SFS = 0, RBS = 0 and endoscopic subscore = 0 over time;
- The achievement of SFS = 0, RBS = 0 and endoscopic subscore ≤ 1 over time;
- The achievement of SFS ≤ 1 , RBS = 0 at Week 28 and clinical remission per Adapted Mayo score at Week 52;
- The achievement of SFS ≤ 1 , RBS = 0 at both Week 28 and Week 52;
- The achievement of SFS ≤ 1 over time;
- The achievement of RBS = 0 over time;
- Change from Baseline in Adapted Mayo score, Full Mayo score, Partial Adapted Mayo score, Partial Mayo score and Mayo subscores over time;
- Change from Baseline in subject-reported stool frequency (absolute values) over time;
- The achievement of histologic improvement at Week 52;
- The achievement of histologic remission at Week 52;
- The achievement of histologic remission at both Maintenance Baseline and Week 52.
- Change from Baseline in histologic score over time;
- The achievement of corticosteroid free over time among subjects taking corticosteroids at Baseline in the Induction Study;
- Change from Baseline in corticosteroid dose over time among subjects taking corticosteroids at Baseline in the Induction Study;
- Change from Baseline in hs-CRP over time;

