8.2.2 UC-Related Rescue Medications

The UC-related rescue medications intercurrent events during the study drug treatment period comprises of the following two intercurrent events,

1. UC-Related corticosteroids intercurrent events are defined as follows:
 - subjects not on UC-related corticosteroids (systemic or locally acting corticosteroids for UC) at Baseline who initiated UC-related corticosteroids during the Maintenance Study;
 - subjects on UC-related systemic corticosteroids at Baseline who had dosages increased to greater than the prednisone equivalent dose of corticosteroid at Baseline, or initiation of any rectal corticosteroids during the Maintenance Study regardless of rectal corticosteroid dose;
 - subjects on UC-related rectal corticosteroids at Baseline who have dosages increased to greater than the dose taken at Baseline, or initiation of any new type of rectal or any systemic corticosteroids during the Maintenance Study.
 - if a subject enters the Maintenance Study without corticosteroids, threshold dose of corticosteroids for censoring will be compared to the Baseline dose of the Induction Study. If subject enters the Maintenance Study with corticosteroids, threshold dose of corticosteroids for censoring will be compared to the dose at Baseline of the Induction Study or at baseline of the Maintenance Study, whichever of the two doses is higher.
2. UC-related non-corticosteroid rescue medications include systemic or rectal use of aminosalicylates, antibiotics and methotrexate. The intercurrent events are defined

as subjects who have initiation or dose escalation of any of these medications compared to Week 0.

The time point of the UC-related rescue medications intercurrent event is defined as the date when one of the intercurrent events above occurs for a subject. For categorical endpoints, subjects will be considered as "non-responder" at or after the occurrence of the UC-related rescue medication intercurrent event through the end of the Maintenance Study except for the As Observed (AO) analysis. For continuous endpoints, all measurements from the date of UC-related rescue medications intercurrent event through the end of the Maintenance Study will not be used in the analysis except for the As Observed (AO) analysis. Methods to handle visits after these intercurrent events are described in Section 8.3.2.

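### Substudy 3: the analysis of change in corticosteroid dose discards every dose recorded after rescue and replaces it with a draw centred on no change, although for this endpoint the rescue event is, or bears directly on, the outcome

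*SAP*

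**What the plan says.** All references are to the Substudy 3 SAP unless stated. Four passages combine.

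- **Endpoint.** Section 3.3 lists "Change from Baseline in corticosteroid dose over time among subjects taking corticosteroids at Baseline in the Induction Study".
- **Method.** Section 8.6 says of the additional endpoints that "The binary endpoints and change from baseline continuous endpoints will be analyzed by CMH and RTB-MI with MMRM/ANCOVA, respectively". Corticosteroid dose is a continuous change from Baseline and is not excepted.
- **Event and exclusion.** Section 8.2.2 counts as rescue "subjects on UC-related systemic corticosteroids at Baseline who had dosages increased to greater than the prednisone equivalent dose of corticosteroid at Baseline". For those entering maintenance on corticosteroids, the threshold is the dose "at Baseline of the Induction Study or at baseline of the Maintenance Study, whichever of the two doses is higher". Other drugs trigger the event too: "UC-related non-corticosteroid rescue medications include systemic or rectal use of aminosalicylates, antibiotics and methotrexate", if started or escalated after Week 0. For continuous endpoints, "all measurements from the date of UC-related rescue medications intercurrent event through the end of the Maintenance Study will not be used", except in the As Observed analysis.
- **Replacement.** Step 2 of Section 8.3.2 says that "missing change from baseline data due to the intercurrent event of UC-related rescue medication will be replaced by a value from a normal distribution" with mean zero. Its variance, Vc, is estimated from the values of all arms that do not follow rescue.

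The Section 8.6 estimand for continuous additional endpoints is the mean difference had rescue medication not been used. The same section analyses UC-related hospitalization and surgery whether or not rescue was used.

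**The concern.** Return-to-baseline imputation makes sense for a symptom or quality-of-life score. Rescue medication can mask the score, and a return to Baseline stands for loss of benefit. Corticosteroid dose is different: rescue does not mask it. When the rescue is a corticosteroid, the dose is the record of that rescue. A subject whose dose rises above the threshold produces the outcome of interest and, by doing so, has it removed. The replacement is centred on the full Baseline dose, whatever was actually taken.

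These doses are not missing in the usual sense. Protocol Sections 5.2.3.2 and 5.2.3.4 require changes in concomitant medication to be entered in the eCRF. The estimand fits no better: corticosteroid dose had no rescue been used is nearly circular when rescue is largely defined by corticosteroid dose, and return-to-baseline does not estimate that quantity either.

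At stake is the size of the steroid-sparing effect on the dose scale, which is compared with placebo at a nominal two-sided 0.05 (Section 12.0).

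**Working it through.** The plan states no figure for this endpoint, so there is none to reproduce. The documents give no rescue rates, Baseline dose distribution or post-rescue doses. All values below are assumptions, except that exclusion criterion 10 (Protocol 5.2.2) caps Baseline oral dose at 30 mg/day prednisone or equivalent.

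**Closed form at one visit.** Let B be the Baseline dose, D the mean dose of rescued subjects at that visit, and p the proportion rescued (U for upadacitinib, P for placebo). Assume unrescued subjects have tapered to zero, a change of -B.

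- Recorded doses: arm mean = (1-p)(-B) + p(D-B) = -B + pD. Arm difference = (pU - pP) x D.
- Planned analysis: arm mean = (1-p)(-B) + p x 0 = -B + pB. Arm difference = (pU - pP) x B.
- Ratio of planned to recorded = B/D. D does not appear in the planned result.

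| B (mg/day) | D (mg/day) | Rescue, placebo vs upadacitinib | Recorded difference (mg/day) | Planned difference (mg/day) |
|---|---|---|---|---|
| 20 | 40 | 40% vs 15% | -0.25 x 40 = -10.0 | -0.25 x 20 = -5.0 |
| 20 | 25 | 50% vs 20% | -0.30 x 25 = -7.5 | -0.30 x 20 = -6.0 |
| 20 | 30 | 50% vs 20% | -0.30 x 30 = -9.0 | -6.0 |
| 20 | 40 | 50% vs 20% | -0.30 x 40 = -12.0 | -6.0 |
| 20 | 0 (tapered off again) | 50% vs 20% | 0 | -6.0 |

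The last four rows differ only in what happened after rescue, and the planned answer does not move.

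**Range.** Take B of 15-20, D of 30-40, rescue of 30-50% on placebo and 10-20% on upadacitinib. The rate difference runs from 0.30 - 0.20 = 0.10 to 0.50 - 0.10 = 0.40.

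- Recorded: -0.10 x 30 = -3 to -0.40 x 40 = -16 mg/day.
- Planned: -0.10 x 15 = -1.5 to -0.40 x 20 = -8 mg/day.
- Ratio: 15/40 = 0.375 to 20/30 = 0.67.

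**Simulation check.** The set-up was 55 subjects per arm, Baseline doses of 5 to 30 mg, rescue 50% vs 20%, 30 imputations, and ANCOVA on treatment and Baseline dose. For true increases of 5, 10 and 20 mg above Baseline in rescued subjects, recorded-dose differences were -6.9, -8.0 and -11.2 mg. The planned method gave -5.4, -5.1 and -5.2 mg. About 50% of the draws were reductions from Baseline in subjects whose dose had risen. About 7.5% fell below minus the Baseline dose, implying a negative dose.

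**The case against.** The case for leaving the plan alone has several parts.

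**Regulatory origin and estimand.** The version history (Section 13.0, version 4.0) says return-to-baseline imputation was adopted on an FDA recommendation and names Section 8.6 among the sections changed; the choice of estimand is the sponsor's. But the documents do not say that the advice considered corticosteroid dose. Table D-4 gives return-to-baseline seeds only for IBDQ and FACIT-F, which suggests this endpoint was overlooked, though a missing seed does not override Section 8.6. The objection here is not a preference between estimands, because the method does not estimate the stated one.

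**Direction.** A reader might infer that the rule always pulls the comparison toward no effect. The documents do not support that. Non-steroid rescue also triggers the exclusion, the exclusion runs to study end, and Protocol 5.2.3.4 encourages tapering of rescue corticosteroids. Discarded doses can therefore lie below Baseline.

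**Scope.** A reader might infer that all corticosteroid increases are removed. They are not: re-increases during the taper at or below the threshold are kept.

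**Other evidence.** A reader might infer that actual doses are never examined, or that steroid-sparing evidence is lost. Section 8.3.2 lists As Observed among the approaches for continuous endpoints, although Sections 8.4.4 and 8.5.2 assign it only to the primary and secondary endpoints and Section 8.6 does not expressly assign it. Ranked secondary endpoint 3 and several additional endpoints use corticosteroid-free status, with rescued subjects counted as non-responders. Concomitant medications are also summarised by arm.

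**Completeness.** Subjects with confirmed loss of response may leave for Study M14-533 (Protocol 5.1.2), so recorded doses need not be complete to Week 52. This stands, and any remedy must deal with it.

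**Conclusion.** The point holds for this one endpoint. It follows from a written rule, not from missing detail: the planned estimate does not depend on any dose recorded after rescue. If rescued subjects stay above their Baseline dose, the arm difference is understated, to 0.375-0.67 of its recorded value under the assumed doses. If they re-taper, it can be overstated, in the extreme showing -6.0 mg/day where recorded doses show none. These sizes rest on assumed rescue rates and doses and on unrescued subjects tapering to zero; the independence from post-rescue doses does not.

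The reach is limited. This is an additional endpoint without multiplicity adjustment, and no primary or ranked secondary result changes. It is worth correcting because the planned figure would be reported as a between-arm comparison of corticosteroid dose, which it would not be.

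**What to change.** In Section 8.6:

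- Exempt change in corticosteroid dose from the Section 8.2.2 exclusion and from return-to-baseline imputation. The same sentence should cover the parallel exclusion in Section 8.2.1, which drops data after study drug is stopped once corticosteroids are started or escalated.
- Analyse all recorded UC-related corticosteroid doses, in prednisone equivalents, regardless of rescue. State a treatment-policy estimand for this endpoint, as Section 8.6 already does for hospitalization and surgery.
- Impute only doses that are truly unrecorded, for example after a subject leaves for Study M14-533, by a method named in the SAP and with a sensitivity analysis.

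The cost is a short SAP edit and a little extra programming, with no new data. The one drawback is that this endpoint would depart from the approach common to the other continuous endpoints.
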